1.3.3 Randomization

The double-blind treatment for each participant will be determined by a predetermined randomization schedule. Participant identification numbers are assigned prior to dosing. Within each site (numbered uniquely within a protocol), participant identification numbers are assigned according to their sequence of presentation for study participation. Individual participant treatment is automatically assigned by the Interactive Voice Response System (IVRS)/Interactive Web Response System (IWRS).

1.3.4 Blinding and Treatment Assignment

The site pharmacy personnel who dispense are not required to be blinded and will not be involved in any study assessment. All participating staff involved in the evaluation and execution of the study will remain blinded to the participant's treatment assignment.

1.3.5 Unblinding the Treatment Assignment

During the study, the treatment assignment must not be broken except in emergency situations in which the identification of the IP is required for further treatment of the participant. If possible, the investigator should contact the Medical Monitor before unblinding. However, this should not delay unblinding in case of an emergency. The investigator should contact the Medical Monitor as soon as possible after the investigator has unblinded the participant.

If the treatment assignment is broken, the date, the signature of the person who broke the code, and the reason for breaking the code are recorded in the source documents. Upon breaking the blinding, the participant will have the follow-up period assessments/procedures, and the follow-up visits/contacts at Week 1, 2, 3, and 4. The IRT (Interactive Response Technology) will record all unblinding events.

2. STATISTICAL CONSIDERATIONS

2.1 General Considerations

- The treatment groups will be coded as “Ganaxolone” and “Placebo,” and all summary tables will be provided by treatment group and overall. When applicable, treatment in open-label phase will be coded as “Openlabel Ganaxolone”.
- In general, descriptive statistics (n, mean standard deviation [SD], median, 25th and 75th percentiles, minimum, and maximum) will be summarized by treatment group for continuous variables. Means and medians will be presented with one more decimal place than the precision of the data. Standard deviations will be presented with two more decimal

places than the precision of the data. Minimums and maximums will be presented with the same precision as the original data.

- Count and percentage of participants in each category will be provided for categorical variables. Unless stated otherwise, percentages are based on the number of participants in the treatment group of the analysis set. Percentages will be presented with one decimal place (xx.x), with the exception of 100%, which will be displayed without any decimal places, and the exception of 0%, which will not be displayed.
- All listings will be listed by treatment group, participant, test parameter, and time point (if applicable).
- Scheduled assessments will be included in summaries. Unscheduled assessments will only be included in the display sections that report abnormal laboratory results, vital signs, or ECG values. Data from all assessments (scheduled or unscheduled), will be included in the listings.
- Unless stated otherwise, baseline is defined as the last non-missing value prior to the first dose of study drug administration.
- P-values will be reported to 3 decimal places, with values less than 0.001 displayed as “<0.001.”
- All outputs should have the following header at the upper left margin:

Marinus Pharmaceuticals, Inc.
Study 1042-SE-3003

And the following header (right justified) at the upper right margin:

Page n of N

Tables/appendices/listing should be internally paginated (i.e., page numbers should appear sequentially within each table). All outputs should have SAS program name, source listing, and execution date and time included in the footnotes.

2.2 Analysis Populations

2.2.1 Safety Population

The Safety Population comprises all participants who received IP. Participants will be analyzed according to the intervention they received.

2.2.2 Intent to Treat (ITT) Population

The ITT Population comprises all randomized participants in the double-blind phase of the study who received IP and had at least one non-missing efficacy assessment. Participants will be analyzed according to the intervention to which they were randomized.

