6.2.2 Allocation of Participants to Treatment

6.2.2.1 Double-Blind Phase

The actual treatment given to individual participants is determined by a randomization schedule. Participant identification numbers are assigned prior to dosing. Within each site (numbered uniquely within a protocol), participant numbers are assigned in the sequence of participant presentation for study participation. To allow for timely delivery of IP to the hospital unit, the IP bottles may be allocated for use in the IRT prior to the participant meeting all eligibility criteria to avoid impact to standard of care. Investigational product will not be administered until eligibility has been determined. Enrollment is defined as the initiation of IP infusion.

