10.3 Analysis Populations

The following population are defined:

Population	Description
Safety	All participants who received IP.
Intent to Treat (ITT)	All randomized participants in the double-blind phase of the study who received IP and had at least one non-missing efficacy assessment.
Per Protocol (PP)	All participants in the ITT population without major protocol deviations related to co-primary endpoint efficacy assessments.
Open-Label (if applicable)	All enrolled participants who received open-label IP (should the study transition to open-label).

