3. STATISTICAL ANALYSIS

3.1 Participant Information

3.1.1 Disposition of Study Participants

The number of participants screened for this study, the number of screen failures and the number of participants who received at least one dose of IP will be summarized using the Enrolled Population. Reasons for screen failure will be provided in the data listing.

Study completion and withdrawal from the double-blind phase will be summarized by treatment group for all enrolled participants. The summary table will include the numbers of participants included in each analysis set and those who completed or did not complete the study, along with the reasons for discontinuation (adverse events, protocol deviation, lost to follow-up, death, etc.) of study treatment and discontinuation from study will be summarized.

Reason for discontinuation from study will be provided in the data listing.

In addition, a summary of the number of participants included in each analysis set will be presented.

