The interim analysis will be performed using the logistic regression method described below. Due to the limited amount of data, the data after the interim analysis will be analyzed using the Boschloo test. If the p-value (one-sided) of the interim analysis is p_1 and the p-value (one-sided) from after the interim analysis is p_2 , and let Φ^{-1} be the inverse Normal function, a final Z score is calculated as

$$Z = \sqrt{\frac{2}{3}}\Phi^{-1}(1 - p_1) + \sqrt{\frac{1}{3}}\Phi^{-1}(1 - p_2)$$

The Z-test using the above Z score will be used as the final test.

The efficacy analysis of the response rates observed for each co-primary endpoint will be conducted by using logistic regression methods. The model will include terms for treatment group and baseline STESS as a covariate. The analysis will be based on the ITT population. Model-based point estimates (i.e., odds ratio), 95% confidence intervals and p-values will be reported. In addition, the point estimate of difference of the proportions of participants achieving either and both co-primary endpoints between two treatment arms will be provided. The 95% confidence interval will be provided using Clopper-Pearson method.

The concerned estimand is defined by its attributes below:

- Population: the target study population comprises participants with status epilepticus who also meet the inclusion and exclusion criteria as specified in the study protocol. The analysis population is the Intent-to-Treat (ITT) population as defined in [Section 2](#).
- Variable for the first co-primary: a binary response variable indicating a successful response which is defined as SE termination beginning within 30 minutes of IP initiation without use of medications for the acute treatment of SE.
- Variable for the second co-primary: a binary response variable indicating absence of IV anesthesia for 36 hours following IP initiation.
- Intercurrent events:
 - Discontinuation of study treatment due to any reason
 - Death
- Population-level summary: odds ratio between treatment groups.

The participants with any of the listed intercurrent events will be considered as a treatment non-responder. To deal with other intercurrent events, a treatment policy approach will be adopted. Due to the nature of the disease and short observational period, occurrence of intercurrent events is expected to be low.

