3.2.1.2 Sensitivity Analysis

The primary efficacy analysis will be repeated in the PP population.

In addition to logistic regression, response rates for both primary endpoints will also be analyzed using the Boschloo test.

If missing data on the first or second co-primary endpoint exceeds 5%, a tipping point analysis will be performed for that endpoint. Assuming N_c participants have missing primary outcome data in the control group and N_t participants have missing primary outcome data in the treatment group, the primary analysis will be performed to assume 0 to N_c control participants achieved the primary outcome and 0 to N_t treatment group participants achieved the primary outcome. All $(N_c+1)(N_t+1)$ outcomes will be enumerated in a grid that shows the treatment effect and p-value and the ‘tipping point’ when the result would cease to be statistically significant. Model averaging will be used to account for multiple possible scenarios contributing to the same number of missing data values.

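### The ITT set requires an undefined efficacy assessment, so a dosed participant whom the SAP estimand counts as a non-responder could be left out of the primary and tipping-point analyses

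*SAP*

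**What the plan says.** Protocol 10.3 defines ITT as "All randomized participants in the double-blind phase of the study who received IP and had at least one non-missing efficacy assessment". SAP 2.2.2 has the same rule: the participant must have "received IP and had at least one non-missing efficacy assessment". Neither text restricts the assessment to the post-dose period.

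The estimand in SAP 3.2.1.1 lists two intercurrent events. One is "Discontinuation of study treatment due to any reason" and the other is death. It then states: "The participants with any of the listed intercurrent events will be considered as a treatment non-responder". It names the ITT set of Section 2 as its analysis population.

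On missing outcomes, SAP 2.5 imputes nothing by default. SAP 3.2.1.2 adds: "If missing data on the first or second co-primary endpoint exceeds 5%, a tipping point analysis will be performed for that endpoint". That analysis re-runs the primary analysis over possible values of the missing outcomes. The other efficacy set, PP (SAP 2.2.3), is a subset of ITT. SAP Table 1 gives primary efficacy no further double-blind population.

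For disposition, SAP 3.1.1 says that screening counts, screen failures and dosed participants "will be summarized using the Enrolled Population", a set that SAP 2.2 does not define. Protocol 6.2.2.1 says: "Enrollment is defined as the initiation of IP infusion".

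**The concern.** The order of operations matters. The population rule decides who is in the analysis, and the non-responder rule then acts only on those who are in. A dosed participant with no qualifying assessment never reaches the second rule, even if the reason is death or IP discontinuation, which the estimand counts as failure. The analyses meant to expose missing-data problems have the same gap, because the 5% trigger, the tipping-point grid and the PP repeat all sit inside ITT.

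At stake is the response rate on both co-primary endpoints. If failures leave one arm more than the other, that arm's rate rises. With 100 randomized, a single participant can matter near the threshold.

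**Working it through.** **Plan figures reproduced.** The spending function at two-thirds information gives 0.05 × (2/3)^(log 2.5 / log 2) = 0.05 × (2/3)^1.322 = 0.0293, as stated. The matching final two-sided level computes to 0.0342, against the stated 0.0343. Power for 75% vs 45% with 62 per arm at two-sided 0.05 is 93.6%, consistent with the stated 90% or more.

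**The two readings.**

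| Reading of the assessment condition | Dosed participant who dies or stops IP before any post-dose assessment |
|---|---|
| Post-dose only | Non-responder by SAP 3.2.1.1, excluded by SAP 2.2.2 |
| Predose counts | Kept and scored as a non-responder |

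The second reading is open because Protocol 7.2.2 lists EEG and STESS under efficacy. EEG is needed for eligibility (Protocol 4.1, criterion 3), and STESS is collected predose.

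**Effect on the 5% trigger (assumed counts).** Take 100 dosed, six of them with unknown outcomes and neither death nor IP discontinuation. Then 6/100 = 6% triggers the tipping-point analysis. If two of the six are excluded for having no assessment, 4/98 = 4.1% does not.

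**Effect on the final test.** SAP 3.2.1.1 combines the one-sided interim logistic p-value p1 with a one-sided Boschloo p-value p2 from later data:

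Z = √(2/3) Φ⁻¹(1 − p1) + √(1/3) Φ⁻¹(1 − p2) = 0.8165 z1 + 0.5774 z2

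Z must exceed 2.117 (two-sided 0.0343). Inputs from the documents are 83 participants at the interim and 100 − 83 = 17 afterwards. Assumptions are arm splits of 42/41 and 8/9, responder counts chosen to be borderline, and an unadjusted Wald p1 without STESS. Counts are ganaxolone vs placebo.

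| Stage 1 | Stage 2 | z1 | z2 | Z | Two-sided p |
|---|---|---|---|---|---|
| 25/42 vs 16/41 | 4/8 vs 2/9 | 1.854 | 0.940 | 2.057 | 0.0397 |
| 25/41 vs 16/41 (one failure dropped) | 4/8 vs 2/9 | 1.971 | 0.940 | 2.152 | 0.0314, crosses |
| 27/42 vs 19/41 | 6/8 vs 4/9 | 1.635 | 1.157 | 2.003 | 0.0452 |
| 27/41 vs 19/41 (one failure dropped) | 6/8 vs 4/9 | 1.768 | 1.157 | 2.111 | 0.0347, does not cross |
| 27/42 vs 19/41 | 6/7 vs 4/9 (one failure dropped) | 1.635 | 1.580 | 2.247 | 0.0246, crosses |

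A third split, 28/42 vs 19/41 with 5/8 vs 4/9, starts at 0.0627. It moves to 0.0484 or 0.0384 when one ganaxolone failure is dropped in stage 1 or stage 2, and neither crosses.

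**Effect on error rate (simplified).** This uses one stage, a pooled z-test, 50 per arm and a true response of 45% in both arms, with exact binomial enumeration. The k dropped participants are all ganaxolone failures; the remaining 50 − k respond with probability 0.45 × 50/(50 − k), so the arm's overall rate stays at 45%. The nominal one-sided level is 0.0343/2 = 0.0172.

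| k | Dropped | Kept as failures |
|---|---|---|
| 1 | 0.021 | 0.017 |
| 2 | 0.027 | 0.016 |
| 3 | 0.036 | 0.016 |
| 5 | 0.053 | 0.015 |

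With two dropped from each arm (run at two-sided 0.05), the rate is 0.026 either way. These figures are for one co-primary endpoint; success requires both.

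**The case against.** The strongest reply is that hardly anyone can be affected. Exclusion requires no efficacy assessment at all. Participants are in hospital, continuous EEG is to run from before IP until 24 hours after it stops, RASS and FOUR are due at 60 minutes, and anesthetics and AEDs are recorded dose by dose (Protocol 5.2). Life expectancy under 24 hours is an exclusion. Stopping IP does not end follow-up (Protocol 4.5.1 and 6.2.7), so anyone who dies or stops IP after a single assessment stays in ITT as a non-responder. All of this stands, and it limits the point to a gap in definition.

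A reader might infer that the condition can only remove failures. The documents do not support that. Assessments could be lost for someone who neither died nor stopped IP, and that outcome is unknown. The non-responder rule is also in the SAP only; Protocol 10.4.1 plans a treatment policy approach. The conflict shown here is therefore with the SAP's estimand.

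A reader might also infer that excluded participants are invisible by arm. They are not. The by-arm disposition table in SAP 3.1.1 covers enrolled, meaning dosed, participants and gives the size of each analysis set. Safety minus ITT is then the number dropped, barring dosing errors, since Safety is as treated and ITT as randomized.

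Finally, the interim has been run on 83 ITT participants, so a change of population could touch p1. That is a real complication for the fix.

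**Conclusion.** The inconsistency holds on the post-dose reading. SAP 2.2.2 and Protocol 10.3 can exclude a dosed participant whom SAP 3.2.1.1 counts as a non-responder, and no planned efficacy analysis brings that participant back. On the predose reading the condition does almost nothing. Neither reading gives a reason to keep it.

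No bias has been shown. Its size depends on an unstated number, probably zero or very small, and on imbalance between arms. The p-values above rest on assumed splits and borderline counts, so they show that one participant can decide the result, not that one will.

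It might be inferred that every missing co-primary outcome should be scored as non-response. That goes further than the conflict requires: death and IP discontinuation already have a rule, and the tipping-point analysis exists for the rest.

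**What to change.** Before final unblinding, and without knowledge of arm:

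1. In SAP 2.2.2 and Protocol 10.3, strike the assessment condition from "who received IP and had at least one non-missing efficacy assessment", so that the primary set is all randomized double-blind participants who started IP.
2. Apply the existing non-responder rule for death and IP discontinuation to that set.
3. Base the 5% trigger and the tipping-point grid on that set, for any other missing outcome.
4. State whether the condition excluded anyone from the interim stage. If it did, assign them to stage 1 by enrollment order and report the combination test twice: with p1 as originally computed and with p1 including them. Say beforehand which of the two decides.
5. In disposition, add randomized participants who were never dosed, by arm, and the reasons for any exclusion from the analysis. Analysis-set counts by arm are already planned.

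The cost is a short wording change in two documents, a small addition to disposition, possibly one extra stage-1 check, and possibly a slightly less favourable response rate. If the condition has excluded nobody, the efficacy results do not change.

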2.2.3 Per Protocol Population (PP)

The PP Population comprises of all participants in the ITT population without major protocol violations or deviations related to co-primary endpoint efficacy assessments. Participants will be analyzed according to the intervention they received.

2.2.4 Open-Label Population

All enrolled participants who receive open-label IP (should the study transition to open label).

2.2.5 Planned Analyses by Study Population

The planned analyses by population are listed in [Table 1](#).

Table 1. Planned Analyses by Study Population

Planned Analysis	Analysis Population			
	Safety	ITT	PP	Open-Label
Demographic and Baseline Characteristics	✓			✓
Medical History	✓			✓
Prior and Concomitant Treatment	✓			✓
Protocol Deviation	✓			✓
IP Infusion Summary	✓			✓
Primary Efficacy		✓	✓	descriptive
Key Secondary Efficacy Analysis		✓	✓	descriptive
Other Secondary Efficacy Analysis		✓		descriptive
Healthcare Utilization Endpoints		✓		descriptive
Safety Analyses	✓			✓

2.3 Time Windows for Analyses

For by-visit safety or efficacy summaries, only scheduled visits will be analyzed. Data collected at unscheduled visits will be provided in listings.

2.4 Pooling of Centers

This multicenter study is to be conducted at approximately 100 sites in the United States, Canada, and Australia. Data from all centers will be pooled for analysis.

2.5 Handling of Missing Data

Unless stated otherwise, there will be no imputation of incomplete or missing data other than the dates mentioned below. Missing efficacy data will be imputed in a sensitivity analysis as described in [Section 3.2.1.1](#).

The handling of partial start and stop dates for AEs are described in [Table 2](#) below. Similar algorithms for handling missing and partial dates of concomitant medication usage are described in [Table 3](#). In both cases, if a stop date is complete and an imputed start date is after the stop date, the start date will be set to the stop date.

Table 2: Adverse Event Start/Stop Date Imputation

Parameter	Missing	Additional Conditions	Imputation
Start date for AEs	D	M and Y same as M and Y of initiation of IP infusion	Date of initiation of IP infusion
		Y same but M prior to month of initiation of IP	Last day of month
		Y same but M after month of initiation of IP infusion	First day of month
		Y is prior to year of initiation of IP infusion	Last day of month
		Y is after year of initiation of IP infusion	First day of month
	M	Y is same as Y of initiation of IP infusion	Month of initiation of IP infusion
		Y is prior to year of initiation of IP infusion	M = December
		Y is after Y of initiation of IP infusion	M = January
	D and M	Y same as Y of initiation of IP infusion	Date of initiation of IP infusion
		Y prior to Y of initiation of IP infusion	M and D will be December 31
		Y after Y of initiation of IP infusion	M and D will be January 1
	Y, or M, D, Y	Y and/or start date missing	Date of initiation of IP infusion
Stop date for AEs	D	M and Y not missing	Use last day of month (i.e., D may take on values of 28, 29, 30, or 31, depending on month)
		Y not missing; if D also missing, impute D as described above	M = December
	Y, or M, D, Y	Y and/or stop date missing.	No imputation. Date left missing.

D=day, M=month, Y=year

Note: In all cases, if an estimated start date is after a complete stop date, the start date will be set to the AE stop date. Similarly, if the estimated stop date is before a complete or imputed start date, use the last day of the start day month.

Table 3: Imputation for Prior/Concomitant Medication Missing and Partial Dates

Parameter	Missing	Additional Conditions	Imputation
Start date for con meds	D only	M and Y are not missing or imputed.	Use 1 st day of M.
	M only	D and Y are not missing or imputed.	M = January
	M and D	Y is not missing or imputed.	Use Jan 01 of Y
	M, D, and Y	None - date completely missing	No imputation but considered concomitant unless stop date is prior to first dose of IP.
Stop date for con meds	D only	M and Y are not missing or imputed.	Last day of month
	M only	D and Y are not missing or imputed.	M = December
	M and D	Y is not missing or imputed	Use Dec 31 of Y
	M, D, and Y	None - date completely missing and NOT ongoing	No imputation

Note: In all cases, if an estimated start date is after a complete stop date, the start date will be set to the end date of medication.

2.6 Analysis Software

All summaries and statistical analyses will be generated using SAS® version 9.4 or later.

2.7 Handling of Data after Interim Analysis

The interim analysis will be conducted based on data from approximately the first 82 participants in the ITT population who have completed assessments for the co-primary and key secondary endpoints. It is anticipated that data cleaning, data analysis, preparation of data and its review by the DMC will require approximately 8-12 weeks. During this time, double-blind randomization will continue.

If the decision is made based on the interim analysis results to discontinue the double-blind phase due to demonstration of efficacy, the analysis set for the primary and key secondary endpoints will consist of data provided to the DMC for review, i.e., approximately 82 participants in the ITT population. Co-primary and key secondary endpoint data for additional double-blind participants enrolled after the interim analysis data cutoff will be summarized in combination with data from the interim analysis using descriptive statistics. Interim efficacy analyses will only be performed for the primary and key secondary endpoints; the analyses of other efficacy endpoints will be performed in the full ITT population in the double-blind phase. Additionally, efficacy endpoint data from the open-label phase will be summarized using descriptive statistics.

If the decision is made at the interim analysis to continue the double-blind phase, safety and efficacy data collected after the interim analysis will be integrated with the interim data and will be included in the final analysis. Safety data from the double-blind and open-label phases will be summarized separately and in combination.

The interim analysis was conducted on the first 83 participants in the ITT population who have completed assessments for the co-primary and key secondary endpoints. The DMC recommended the study may continue without modification.

